1.23 Study design

The proposed research project involves primary and several secondary objectives. To address these aims, we will conduct a single-blinded, randomized, parallel group trial. Step counts, activity, 6MWT, emPHasis-10, echo, proton MRS, muscle function test, and blood sampling will be performed at screening and 12 weeks. Disposition of subjects and screening comparisons will be reported.

Summaries of all subjects screened, recruited, and randomized and the number who complete the week 12 visit post-randomization will be provided, according to the CONSORT guidelines. The treatment groups will be compared at baseline with respect to demographics and baseline measurements related to efficacy and safety without formal statistical testing.

1.24 Statistical Analysis

The primary analyses will focus on metformin vs placebo, exercise vs placebo, and metformin + exercise vs placebo comparisons on the primary endpoint. Since the evaluation of metformin or exercise will be reported as if they were independent studies and the combination arm versus placebo comparison serves to corroborate findings of the two separate comparisons, in addition to evaluating an additive or synergistic effect, we will not adjust for multiple comparisons. For binary endpoints, the Pearson chi-square or Fischer's exact test will be used to assess between treatment arms difference. Logistic regressions will be conducted to examine the treatment effect while adjusting for important covariates such as baseline 6MWD, functional status, age, and study site. Model over-fitting will be avoided by considering the number of parameters in the model and the number of responders in the sample. Continuous endpoints will be analyzed using either two-sample t-test or ANOVA, or non-parametric methods Wilcoxon Rank Sum test or Kruskal-Wallis test. Multivariable regressions (general linear models) will be conducted to examine the treatment effect while adjusting for important covariates such as baseline 6MWD, functional status, age, and study site. We have designed the study to minimize the potential for missing data. Subjects who drop out will be replaced up to a total of 35 per group. Nevertheless, in the event we have missing data, a multiple-imputation procedure as implemented in the aregImpute function in the Hmisc package in R (R Package; Version 3.0-10) will be used to assess the impact of missing data. The analyses with imputation will mainly serve as sensitivity analyses.

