- To assess the effect of a mHealth intervention or no intervention and/or metformin or placebo on dropout rates over 12 weeks.
- To assess the effect of a mHealth intervention or no intervention and/or metformin or placebo on PAH-related hospitalizations over 12 weeks.
- To assess the effect of a mHealth intervention or no intervention and/or metformin or placebo on medication regimen escalation/reduction over 12 weeks.
- To assess the effect of a mHealth intervention or no intervention and/or metformin or placebo on incidence of death over 12 weeks.

STUDY DESIGN:

A 2x2 factorial randomized, blinded trial testing metformin versus placebo and an mHealth intervention (mHealth) versus usual care for 12 weeks.

STUDY POPULATION:**Inclusion criteria:**

- Adults aged 18 or older.
- Diagnosed with idiopathic, heritable, connective tissue disease – associated PAH , or drug- or toxin-associated pulmonary arterial hypertension (PAH) according to World Health Organization consensus recommendations.
- Repaired simple congenital heart disease or unrepaired ASD
- Stable PAH-specific medication regimen for three months prior to enrollment. Subjects with only a single diuretic adjustment in the prior three months will be included. Adjustments in IV prostacyclin for side effect management are allowed.
- Subjects must own a Bluetooth capable modern smartphone capable of receiving and sending text messages and an active data plan.
- FEV1 $>$ or = 60% predicted and no more than mild abnormalities on lung imaging
- WHO Functional Class I-III
- Ambulatory

Exclusion criteria:

- Prohibited from normal activity due to wheelchair bound status, bed bound status, reliance on a cane/walker, activity-limiting angina, activity-limiting osteoarthritis, or other condition that limits activity
- Pregnancy
- Diagnosis of PAH etiology other than idiopathic, heritable, connective tissue disease – associated PAH, or associated with drugs or toxins
- Drug and toxin associated PAH patients with active drug use
- WHO Functional class IV heart failure
- FEV1 $<$ 60% predicted with more than mild abnormalities on lung imaging
- Requirement of > 1 diuretic adjustment in the prior 30 days
- Preferred form of activity is not measured by an activity tracker (swimming, ice skating, stair

master, or activities on wheels such as bicycling or rollerblading)

- Type I diabetes mellitus
- Prior diagnosis of cirrhosis
- Untreated hypo- or hyper-thyroidism
- eGFR by MDRD <40mL/min

PRIMARY ENDPOINT:

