1.26 Statistical Power

The pivotal trial of Iloprost demonstrated that in the Iloprost arm nearly 40% had 10% improvement in 6MWD, 50% had improved FC, and 17% had both¹. From these data we calculate that 73% had either 10% improvement in 6MWD or improved functional status. Assuming metformin or the exercise arm will have similar response rate, and the placebo group will have 40% response rate, thought to be due to training effect potentially, we need 35 per group to have 80% power at 0.05 type I error rate. For the metformin and exercise combination group, an additive or synergistic effect between the two interventions will put its response rate above 73%. Thus, the combination vs. placebo comparison will have at least 80%, likely better power. From past experience coupled with the low risk, low side effect profile interventions, we estimate a dropout rate of less than 10%¹. We will enroll 40 subjects to ensure 35 completed subjects per group. The total target enrollment is 160 over 4.5 years.

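### The 2x2 factorial trial pre-specifies no main effect or interaction for its primary endpoint, and its reason for unadjusted, corroborating tests fails because all three tests share one control arm

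*Combined protocol and SAP*

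**What the plan says.** The Protocol Summary (Study Design) describes "A 2x2 factorial randomized, blinded trial testing metformin versus placebo and an mHealth intervention (mHealth) versus usual care for 12 weeks", and sections 1.7 and 1.11 say the same. Section 1.10 randomises 40 subjects to each of four arms, stratified by WHO functional class (I/II v III).

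For the primary endpoint, section 1.24 and the Summary's Data Analysis paragraph say: "The primary analyses will focus on metformin vs placebo, exercise vs placebo, and metformin + exercise vs placebo comparisons on the primary endpoint". Section 1.26 powers one active group against the placebo group at 35 completers per group and treats the combination as a further group, so each comparison is arm against arm. The test is given as: "For binary endpoints, the Pearson chi-square or Fischer's exact test will be used to assess between treatment arms difference".

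The reasoning on multiplicity begins "Since the evaluation of metformin or exercise will be reported as if they were independent studies", adds that "the combination arm versus placebo comparison serves to corroborate findings of the two separate comparisons, in addition to evaluating an additive or synergistic effect", and concludes "we will not adjust for multiple comparisons".

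For the combination, section 1.26 expects that "an additive or synergistic effect between the two interventions will put its response rate above 73" per cent, without giving a figure. Neither a main effect pooled over the other factor nor an interaction term appears anywhere. Covariate-adjusted logistic and linear models are planned, but the text does not say whether they pool the four arms or carry factor terms.

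**The concern.** Two things are at stake.

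First, metformin is randomised twice: metformin alone v double control, and combination v mHealth alone. Only the first contrast is used to judge metformin, and the same holds for mHealth. An analysis using both contrasts costs no subjects, and would help most if the 73% response rate, taken from a trial of another drug, proves optimistic.

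Second, treating the two evaluations as separate studies and the combination as corroboration invites a reader to count three favourable results as three pieces of evidence. All three are measured against the same 35 people. A control arm that responds poorly by chance pushes all three the same way.

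The plan also gives the combination v control test the task of evaluating an additive or synergistic effect. That test cannot do so, because it does not involve the single-agent arms.

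**Working it through.** **Inputs.** Control response 40%, single-agent response 73%, 35 completers per group, 80% power, alpha 0.05 (all section 1.26). Two-sided testing is assumed, since the plan does not state it. The combination rate is not given, so it is varied.

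**1. The plan's own figure.** Either component: 0.40 + 0.50 − 0.17 = 0.73. With pooled variance and mean rate 0.565:

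n = [1.960·√(2×0.565×0.435) + 0.842·√(0.40×0.60 + 0.73×0.27)]² / 0.33² = (1.374 + 0.556)² / 0.1089 ≈ 34.2, so 35 per group.

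The figure reproduces. Exact binomial power at 35 v 35 is 79.8% for Pearson chi-square and 72.7% for Fisher's exact test.

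**2. Data used.** Metformin alone v control uses 35 + 35 = 70 of 4 × 35 = 140 completers. A main effect compares 70 with 70. At a common 40% rate, the standard error of the risk difference is √(2×0.24/35) = 0.117 pairwise and √(2×0.24/70) = 0.083 for the main effect.

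**3. Dependence.** The two single-agent differences share the control proportion, so their covariance is the control arm's variance. With equal arm sizes the correlation is v₀/(v₀ + v₁), where v = p(1 − p):
- under the null: 0.24/(0.24 + 0.24) = 0.50;
- at 40% v 73%: 0.24/(0.24 + 0.197) = 0.55.

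For the two main effects the covariance is proportional to v(combination) + v(control) − v(metformin) − v(mHealth), which is 0 under the null.

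**4. False positives with all arms at 40%** (exact enumeration, Pearson tests).
- One given single-agent test falsely favourable: 2.418%.
- Both falsely favourable: 0.545%, against 0.024² ≈ 0.06% if independent.
- Conditional probability: 0.545/2.418 = 22.5%. With factorial main effects it is under 3% by simulation.
- Any false positive, normal approximation with correlation 0.5: 9.1% for two tests and 12.5% for three, against 9.75% and 14.3% if independent. Sharing the control slightly lowers this risk.

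**5. Main-effect power.** Mantel-Haenszel test of one factor stratified by the other, 35 completers per arm, by simulation. WHO-class stratification was not modelled. For log-odds additivity at 73%: OR = (0.73/0.27)/(0.40/0.60) = 4.06; combination odds = 0.667 × 4.06² ≈ 10.97, a rate of 91.6%. The same formula gives 83.8% when single agents respond at 65%, and 77.1% at 60%.

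| Single-agent rate | Combination rate | Pairwise power | Main-effect power |
|---|---|---|---|
| 73% | 91.6% (log-odds additive) | 80% | 94% |
| 73%, other agent inactive (40%) | 73% | 80% | 98% |
| 65% | 83.8% (log-odds additive) | 54% | 80% |
| 60% | 77.1% (log-odds additive) | 36% | 62% |
| 73% | 82.5% | 80% | 80% |
| 73% | 80% | 80% | 74% |
| 73% | 73% | 80% | 55% |
| 65% | 65% | 54% | 32% |
| 60% | 60% | 36% | 22% |

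**6. Interaction.** Additivity is judged by p(combination) − p(metformin) − p(mHealth) + p(control), not by combination v control. On the risk scale the planned rates cannot be fully additive: 0.40 + 0.33 + 0.33 = 1.06. At a 40% rate the standard error of this contrast is √(4×0.24/35) = 0.166, so its 95% interval is about ±32 percentage points.

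**The case against.** The primary aim in section 1.7 asks about each intervention and about both combined, and the pairwise tests answer exactly that. Simple effects are a recognised choice where interaction is contemplated, and the plan names synergy. This stands, and it is why the pairwise tests should remain primary.

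The gain from main effects depends on a rate the plan does not give. Between 73% and about 82% for the combination, all of which section 1.26 permits, the main effect has less power than the pairwise test. Both interventions target insulin resistance, so overlap is plausible. This stands too, and rules out making main effects the sole primary analysis.

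Section 1.24 says only that the evaluations will be reported as if independent, which is a reporting convention rather than a claim about test statistics. That is a fair reading, but the convention is the stated ground for not adjusting, and calling the combination test corroborating goes further. Joint false positives are rare in absolute terms (0.54%); the problem is how a joint positive result would be read.

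A reader might also infer three things that the documents do not support:
- Precision is lost on secondary and safety endpoints. Section 1.24 confines the three comparisons to the primary endpoint, allows ANOVA and linear models for continuous endpoints, and sets no safety contrast. The contrast is unstated, which is not the same as pairwise.
- Sharing a control inflates the chance of a false positive. It does not (step 4).
- Section 1.23 contradicts the factorial design where it says "we will conduct a single-blinded, randomized, parallel group trial". A factorial trial is also a parallel-group trial, as opposed to a crossover.

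**Conclusion.** The point holds as an omission and a faulty rationale. It does not show that the trial is underpowered or its primary tests invalid: 35 per group is correct for the tests planned, assuming two-sided Pearson tests.

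Each single-intervention primary test leaves out half of the completers, and nothing pre-specified uses them for that question. The independence and corroboration argument fails because the tests correlate at 0.50 under the null, so a second favourable result adds much less than a separate study would.

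Adding main effects gives 94% or 98% power in the two favourable cases at 73% response, and 80% v 54% or 62% v 36% if single-agent response is 65% or 60% with log-odds additivity. The advantage reverses below a combination rate of about 82–83% when single agents respond at 73%. These figures assume 35 completers in every arm and a 40% control rate.

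**What to change.** In section 1.24 and the Summary's Data Analysis paragraph:

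1. Keep the three pairwise tests as primary.
2. Pre-specify, as key supportive analyses, the main effect of each factor in all randomised subjects with outcome data: metformin (alone or combined) v no metformin, and mHealth (alone or combined) v no mHealth. Use CMH or logistic regression stratified by the other factor and by WHO-class stratum.
3. Report the interaction estimate with its confidence interval beside them and name the scale. Given its width, a non-significant interaction should not be taken as proof of additivity.
4. For continuous endpoints, where the contrast is unstated, use the same two-factor structure in the linear model, again with the interaction estimate.
5. Replace the independence rationale with a statement that the three comparisons share a control arm, are unadjusted, and are not independent corroboration. Assign the question of additivity or synergy to the interaction estimate.

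The cost is wording and a few extra models, with no additional subjects, visits or data. The change should be dated before outcomes are compared by arm, since main effects added later would look post hoc. The remaining downside is dilution of the main effect if effects are sub-additive. Keeping the pairwise tests primary protects the primary conclusion from this, and reporting the interaction shows the reader how far the supportive and continuous-endpoint results may be affected.

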1.11 Overview

We propose a phase II, 2x2 factorial randomized, blinded trial testing metformin versus placebo and an mHealth intervention (mHealth) versus usual care of 12 weeks.

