1.27 Interim Monitoring Guidelines

We have not planned formal interim analyses for efficacy and therefore there are no stopping rules for efficacy for this trial. This is a Phase II trial which will be useful in supporting future studies of the intervention even if null. This project will have a DSMB who may consider whether to stop the trial or not if there is an increased risk of adverse events or toxicity.

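### Combination versus placebo cannot on its own evaluate an additive or synergistic effect, and the plan names no interaction estimate, combination-versus-single contrast or scale that would

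*Combined protocol and SAP*

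**What the plan says.** Section 1.11 describes the design: "We propose a phase II, 2x2 factorial randomized, blinded trial testing metformin versus placebo and an mHealth intervention" against usual care. Section 1.10 allocates participants to one intervention, both or neither, 40 per arm.

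Section 1.24 sets out the primary analysis: "The primary analyses will focus on metformin vs placebo, exercise vs placebo, and metformin + exercise vs placebo comparisons on the primary endpoint". It then says that the "combination arm versus placebo comparison serves to corroborate findings of the two separate comparisons, in addition to evaluating an additive or synergistic effect". The Data Analysis paragraph of the Protocol Summary contains the same statement.

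For binary endpoints the plan names a Pearson chi-square or Fisher's exact test, which "will be used to assess between treatment arms difference". It adds regression: "Logistic regressions will be conducted to examine the treatment effect while adjusting for important covariates such as baseline 6MWD", with functional status and age, and with study site in section 1.24 only. No metformin-by-mHealth product term is listed. Neither section 1.24 nor any other section names a combination-versus-metformin or combination-versus-mHealth contrast, or a scale on which additivity would be judged.

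Section 1.26 bases the sample size on "Assuming metformin or the exercise arm will have similar response rate, and the placebo group will have 40% response rate". The single-intervention rate is 73%. The combination rate is given only as something above 73%, and that statement supports a lower bound on power against placebo.

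**The concern.** Additivity and synergy are statements about how the combination compares with what the two single interventions would lead one to expect. A comparison of the combination arm with the no-intervention arm contains no information from either single-intervention arm. It estimates the joint effect of giving both. That effect can be large because one intervention works and the other adds nothing to it, because the two partly overlap, or because they add fully.

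The text therefore credits this contrast with something it does not deliver, and does so in two places. A favourable combination result could be described as additive or synergistic, with the plan cited in support, when the combination is no better than either intervention alone. Because no scale is fixed, the scale could also be chosen after the data are seen.

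**Working it through.** **Inputs.** From section 1.26: 35 completers per arm, control rate 0.40, single-intervention rate 0.40 + 0.50 − 0.17 = 0.73, type I error 0.05, power 80%. Sidedness is not stated; two-sided is assumed because it reproduces the plan's number. The combination rate is given only as above 73%, so 0.73 is used as the boundary where nothing is added, and 0.80 and 0.85 are illustrative assumptions. Placebo is read as the arm receiving neither intervention, following section 1.10.

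**1. The plan's own figure.** Pooled-variance formula, mean rate 0.565:
n = [1.96·√(2·0.565·0.435) + 0.8416·√(0.40·0.60 + 0.73·0.27)]² / 0.33² = (1.374 + 0.556)² / 0.1089 = 34.2, rounded up to 35. Power at 35 per arm is 80.9% by the same approximation and 79.8% by exact enumeration of the uncorrected Pearson test. The sample size is reproduced.

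**2. What the combination contrast detects.** Exact rejection rate against the 40% control arm, 35 per arm:

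| Combination rate | Rejects against control |
|---|---|
| 73% (nothing added) | 79.8% |
| 80% (assumed) | 94.2% |
| 85% (assumed) | 98.5% |
| 91.6% (log-odds additive, step 4) | 99.9% |

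The first row equals the power for a single intervention, because the two rates being compared are the same. A significant result is the usual outcome in every row, so it does not distinguish them.

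**3. The interaction in the first row.** Odds are 0.40/0.60 = 0.667 in the control arm and 0.73/0.27 = 2.704 in the other three. Interaction odds ratio = (2.704 × 0.667) / 2.704² = 0.667 / 2.704 = 0.25. This is strongly sub-additive on the odds scale, in a setting where the contrast rejects about 80% of the time.

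**4. What additive would mean.** Combination rate implied by no interaction, at 40% and 73%:
- Multiplicative non-response: 1 − 0.27²/0.60 = 0.8785, or 87.9%.
- Log-odds: odds = 2.704²/0.667 = 10.96, giving 10.96/11.96 = 91.6%.
- Risk difference: 0.40 + 0.33 + 0.33 = 1.06, or 106%, which cannot occur.

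At these rates an observed 90% would be more than additive on the first scale and less than additive on the other two. On the risk-difference scale every possible result would be sub-additive.

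**5. What a proper estimate could offer at 35 per arm.** For the log-odds interaction, SE = √[Σ 1/(35·p(1−p))] over the four arms.
- Combination 73%: SE = √[(4.167 + 3 × 5.074)/35] = 0.744; log ratio −1.400; expected 95% CI for the ratio about 0.06 to 1.06; power about 47%.
- Combination 80%: log ratio −1.008, SE 0.767; power about 26%.
- Combination 85%: log ratio −0.660, SE 0.796; power about 13%.
- Combination 91.6% (no interaction): SE 0.884; expected 95% CI about 0.18 to 5.7.

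For combination against one single arm, exact power is 10% at 80%, 23% at 85% and 55% at 91.6%. The 95% CI half-width for the difference is 17 to 21 percentage points over combination rates from 73% to 91.6%.

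**The case against.** The best defence has three parts, and much of it stands.

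First, the contrast is not presented alone. On a linear scale, combination minus control, less metformin minus control, less exercise minus control, is the interaction, and differences between the planned contrasts give combination against each single arm. So a reader who inferred that the planned analyses are incapable of addressing additivity would go too far. The contrast is one necessary component. What is missing is any statement that the components will be put together, and on which scale.

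Second, significance alone understates what the data would show. With singles at 73%, the observed combination rate exceeds both observed single-arm rates in 28% of trials when the true combination rate is 73%, and in 95.5% when it is 91.6%. The arm rates do help to separate the extremes. That is informal description, though, and it shows superiority to the singles rather than additivity.

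Third, the clause is subordinate. Its sentence concludes with the decision on multiplicity ("in addition to evaluating an additive or synergistic effect, we will not adjust for multiple comparisons"), and no listed objective, aim or endpoint asks about additivity or synergy. The three contrasts answer the primary aim as stated. This limits the importance of the point but does not make the clause correct.

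A reader might also infer that the sponsor intends to declare synergy from a significant combination result. Nothing in the documents says so. Nor does section 1.27, "This is a Phase II trial which will be useful in supporting future studies of the intervention even if null", create a requirement to establish what a second intervention adds: it explains the absence of efficacy stopping rules.

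**Conclusion.** The point holds as a mismatch between a stated purpose and the analysis assigned to it. On its own, combination versus placebo cannot evaluate additivity or synergy. At the plan's rates it would reject about 80% of the time with nothing added over either intervention. The plan leaves open both the estimate that would address the question and the scale, and the scale moves the additive combination rate from 87.9% to 91.6% to an unattainable 106%.

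The figures rest on 35 completers per arm, the plan's 40% and 73%, and a two-sided 0.05 test. Combination rates of 80%, 85% and 91.6% are not in the documents.

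It would be wrong to conclude that the primary analysis or the sample size is in error. The three pairwise contrasts fit the primary aim, 35 per arm is reproduced, and the expectation of a combination rate above 73% is adequate support for a power floor against placebo. The decision not to adjust for multiplicity is not challenged here. It is worth correcting before analysis because it is cheap and because the present wording would support a claim that the contrast cannot bear.

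**What to change.** In the Data Analysis paragraph of the Protocol Summary and in section 1.24, remove the clause that gives combination versus placebo the additive or synergistic role, and say instead that this contrast estimates the joint effect of both interventions against neither.

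That is sufficient if the sponsor does not want to pursue the question. If it does, pre-specify as exploratory:
- the metformin-by-mHealth interaction estimate with a 95% CI, from a four-arm model with both factors and their product, on a named scale;
- the difference between the combination arm and each single-intervention arm, with 95% CIs;
- a statement that these are low-power estimates, so that an interval including no interaction is not taken as evidence of additivity.

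The cost is a wording change in two places and, if the question is kept, one model term and two differences from data already collected. No participants, visits or measurements are added. The downside is imprecision: the interaction interval would run from about 0.18 to 5.7 if the effects are additive on the log-odds scale. The three pairwise primary contrasts, the sample size and the decision not to adjust for multiplicity stay unchanged.
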